### **12.5.2 Safety endpoints**

For all safety analyses, the safety set will be used. All listings and tables will be presented by treatment group.

Summary tables for AEs will summarize only on-treatment events, with a start date during the on-treatment period (TEAEs). The on-treatment period lasts from the date of first administration of study treatment to 30 days after the date of the last actual administration of any study treatment.

The secondary endpoint for safety is the frequency of TEAEs and TESAEs in all subjects.

The number (and proportion) of subjects with TEAE will be summarized in the following ways:

[figure not shown]
[figure not shown]
- Overall summary of subjects with any TEAE, any severe TEAE, any study drug related TEAE, any TEAE leading to study drug discontinuation, any TESAE, any study drug related TESAE
- TEAE by primary system organ class and preferred term
- TEAE by descending frequency and preferred term for ocular and non-ocular respectively
- TEAE by maximum severity
- TESAE by primary system organ class and preferred term
- Study drug related TESAE by system organ class and preferred term

[figure not shown]
Any other AEs or SAEs will be listed.

A subject with multiple adverse events within a primary system organ class is only counted once towards the total of the primary system organ class.

### **Vital signs**

All vital signs data will be listed by treatment group, subject, and visit/time. Summary statistics will be provided by treatment and visit/time.

## **12.7 Interim analyses**

Not applicable.

[figure not shown]
[figure not shown]
## **12.8 Sample size calculation**

### **12.8.1 Primary endpoint(s)**

Assuming a mean difference of 4.9 ETDRS letters with a common standard deviation of 6.02 ETDRS letters in change from baseline in binocular DCNVA at 3 months between UNR844 and placebo, based on the results of the prior study in presbyopic subjects, 66 subjects (33 in each arm) aged 45 to 55 years are required to complete the study to achieve an approximate power of 94% at 5% (one-sided) significance level. Assuming about 90% subjects will complete the study, a total of 72 subjects for the primary efficacy endpoint will be enrolled.

### **12.8.2 Secondary endpoint(s)**

Assuming the proportion of subjects achieving 75 or more ETDRS letters in binocular DCNVA at Month 3 are 40.5% and 10.5% for UNR844-CI and placebo, respectively, based on the results of the prior study in presbyopic subjects, 66 subjects (33 in each arm) aged 45 to 55 years are required to be completed to achieve an approximate power of 82% at 5% (one-sided) significance level.

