### **6.3.2 Treatment assignment, randomization**

At baseline visit, all eligible subjects will be randomized via IRT to one of the treatment arms. The investigator or his/her delegate will contact the IRT after confirming that the subject fulfills all the inclusion/exclusion criteria. The IRT will assign a randomization number to the subject, which will be used to link the subject to a treatment arm and will specify a unique medication number for the first package of study treatment to be dispensed to the subject.

The randomization numbers will be generated using the following procedure to ensure that treatment assignment is unbiased and concealed from subjects and investigator staff. A subject randomization list will be produced by the IRT provider using a validated system that automates the random assignment of subject numbers to randomization numbers. These randomization numbers are linked to the different treatment arms, which in turn are linked to medication numbers. A separate medication list will be produced by or under the responsibility of Novartis

Global Clinical Supplies using a validated system that automates the random assignment of medication numbers to packs containing the study treatment.

Randomization will be stratified based on binocular DCNVA (59 ETDRS letters or less; 60 ETDRS letters or more) and age (45 to 50 years, 51 to 55 years and 56 to 65 years) at baseline.

Subjects will be randomized 1:1 within each stratum to either UNR844-CI or placebo.

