##### **12.5.1 Efficacy endpoint**

The secondary efficacy endpoint, the proportion of subjects aged 45 to 55 years achieving 75 or more ETDRS letters in binocular DCNVA at Month 3, is based on the data observed in the FAS population, according to the treatment group patients was randomized and the DCNVA stratum that was assigned at randomization. The comparison between the two treatment groups will be performed using stratified Cochran-Mantel-Haenszel test at one-sided 5% level of significance.

Assuming the following hypotheses will be tested:

$$H_0: \delta_2 = 0 \text{ vs. } H_a: \delta_2 > 0$$

where  $\delta_2$  is the difference of proportion of subjects achieving 75 or more ETDRS letters in binocular DCNVA between the UNR844-C1 and placebo at Month 3.

The estimand for the secondary efficacy endpoint is closely related to the estimand for the primary efficacy endpoint. For subjects who has a DCNVA assessment at Month 3, the observed letter score will be used to derive the endpoint of achieving 75 or more ETDRS letters or not. For subjects who has no DCNVA assessment at Month 3, the predicted value of the estimand

for the primary efficacy endpoint will be used to derive the endpoint of achieving 75 or more ETDRS letters or not.

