2.7.2 Statistical hypothesis, model, and method of analysis

The analysis of the secondary efficacy endpoint is based on the data observed in the FAS population, according to the treatment group subjects was randomized and the DCNVA stratum that was assigned at randomization. The comparison between the two treatment groups will be performed using stratified Cochran-Mantel-Haenszel (CMH) test at one-sided 5% level of significance, with stratified baseline DCNVA and age group as the stratification factors. Alternatively, if the cell count for any of the strata is too small (e.g., <5), the analysis will be done separately for each of the two stratification factors.

Assuming the following hypotheses will be tested:

$$H_0: \delta_2 = 0 \text{ vs. } H_a: \delta_2 > 0$$

where δ_2 is the difference of proportion of subjects achieving 75 or more ETDRS letters in binocular DCNVA between the UNR844-CI and placebo at Month 3.

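### Is the 82% power stated for the secondary endpoint wrong, given that the planned one-sided 5% CMH test has about 89% to 90%?

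*Protocol*

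**What the plan says.** Protocol 12.8.2 takes responder rates at "Month 3 are 40.5% and 10.5% for UNR844-CI and placebo, respectively". It states that 66 subjects in the 45 to 55 age group, 33 per arm, "are required to be completed to achieve an approximate power of 82% at 5% (one-sided) significance level". SAP 3.1.2 repeats the statement. Neither section names the test or formula behind the figure, or says whether a continuity correction was used.

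The analysis is described elsewhere. Protocol 12.5.1 has the comparison "performed using stratified Cochran-Mantel-Haenszel test at one-sided 5% level of significance". SAP 2.7.2 stratifies it "with stratified baseline DCNVA and age group as the stratification factors", which SAP 5.2.2 turns into four strata. The SAP code takes the CMH statistic from PROC FREQ, with no continuity correction.

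Protocol 12.8.1 derives the 72 subjects to be enrolled in this age group from the primary endpoint. SAP 2.6 states that the study has no key secondary objective.

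**The concern.** A power figure is normally read as belonging to the planned test. Most statisticians would check this one with the uncorrected two-proportion formula, the usual large-sample stand-in for a CMH test. At one-sided 5% that gives 89%, not 82%. The same formula at two-sided 5% gives 81.3%, close enough to 82% to suggest that a two-sided calculation was labelled one-sided.

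If that were so, the plan would misstate an operating characteristic in both documents, and the error rate for which the endpoint was sized would be in doubt. The claim that 66 completers are needed would also fail, because 27 per arm (54 in total) already give 82% with the uncorrected one-sided formula.

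**Working it through.** **Inputs** (Protocol 12.8.2, repeated in SAP 3.1.2)
- p1 = 0.405, p2 = 0.105, difference d = 0.30, mean rate p̄ = (0.405 + 0.105)/2 = 0.255.
- n = 33 completers per arm. Allocation is 1:1 (Protocol 6.3.2: "Subjects will be randomized 1:1 within each stratum to either UNR844-CI or placebo"). The 10% dropout allowance does not enter, because the figure refers to completers.
- One-sided α = 0.05, so z = 1.645.

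**Standard errors at n = 33**
- Null (pooled): s0 = √(2 × 0.255 × 0.745 / 33) = 0.1073.
- Alternative: s1 = √((0.405 × 0.595 + 0.105 × 0.895) / 33) = 0.1007.

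**Step 1: reproduce the plan's figure.** With continuity correction 1/n, power = Φ[(d − 1/n − z·s0)/s1].
- n = 33: (0.30 − 0.0303 − 1.645 × 0.1073)/0.1007 = 0.925, and Φ(0.925) = **82.3%**.
- n = 32: s0 = 0.1090, s1 = 0.1023. (0.30 − 0.03125 − 1.645 × 0.1090)/0.1023 = 0.875, and Φ(0.875) = **80.9%**.

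Solving for n at 82% power gives the same answer. The uncorrected size is n′ = (1.645·√(2 × 0.255 × 0.745) + 0.915·√(0.405 × 0.595 + 0.105 × 0.895))² / 0.30² = 26.5. The corrected size is (n′/4)·[1 + √(1 + 4/(n′d))]² = 32.8, rounded up to **33 per arm**.

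**Step 2: the figure that raises the doubt.** Without the correction, (0.30 − 1.645 × 0.1073)/0.1007 = 1.226, and Φ(1.226) = 89.0%. Exact enumeration of the CMH statistic in a single stratum gives 90.3%. Simulation with two or four equal strata unrelated to response gives 89.9%. Strata that predict response raise it to about 91% to 95.5%, under assumed shifts on the logit scale with the marginal rates held fixed.

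**Step 3: which basis fits the stated pair of 82% and 33 per arm?**

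| Basis | Power at n = 33 | n per arm for 82% |
|---|---|---|
| One-sided 5%, continuity-corrected | 82.3% | 33 |
| One-sided 5%, uncorrected | 89.0% | 27 |
| Two-sided 5%, uncorrected | 81.3% | 34 |

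Of these three, only the first returns both stated numbers, and it uses the sidedness that the documents state. The 27 per arm comes from changing the formula; with the correction, 27 per arm gives 72.9%.

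**Step 4: other conservative methods at one-sided 5%, n = 33.** Fisher's exact test has 83.6% power by exact enumeration, and a log odds ratio approximation gives 83.7%. A value in the low eighties is therefore ordinary for this comparison.

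**The case for a change.** The strongest counter-argument is that a stated power should belong to the declared test or name the test that it does belong to. The only test declared for this endpoint is the CMH test, and 82% is not its power at one-sided 5% without a correction. That arithmetic is correct, and stratification does not close the gap, since prognostic strata raise the power.

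The argument continues that the basis matters because the SAP code is itself unclear on sidedness. SAP 5.2.2 selects method 2, whose p-value is the upper tail of a pooled chi-square-type statistic. It has no direction and is not halved, whereas the unused method 1 does convert to one-sided. Compared with 0.05, the method 2 p-value acts as a one-sided 2.5% test in the favourable direction. Its power is then 81.9% (exact, single stratum, ignoring imputation).

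That observation about the code stands, but it is a separate point about how the p-value is made one-sided and does not make the power statement wrong. It also weakens the case for 89%, which is the power of the test described in the text, not of the code as written. Nor is 89% a uniquely right replacement. It leaves out the gain from prognostic strata, the multiple imputation and pooling, and the SAP 2.7.2 fallback to separate stratification when cells are small.

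What remains is that the formula and its continuity correction are not named. That is missing detail of modest use to a reader.

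**Conclusion.** The concern does not hold. The stated 82% follows from the stated rates, size, level and sidedness by a standard formula (82.3%), and 33 per arm is the smallest size at which that formula reaches 82%. The gap of about 7 to 8 points to the uncorrected CMH figure (89.0% to 90.3%) is the effect of the continuity correction. Sizing with a conservative two-proportion formula and analysing with CMH is a choice between approximations, and the text claims only approximate power. Sidedness is stated in both documents.

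The discrepancy has no practical consequence. It understates the power of the test as described, so it hides no shortfall, and the enrolment of 72 comes from the primary endpoint.

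Two assumptions underlie this. The documents do not name the formula, so the continuity correction is inferred from the fit of both numbers. The 89.0% to 90.3% range takes strata unrelated to response and ignores imputation.

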## **13 Ethical considerations and administrative procedures**

### **13.1 Regulatory and ethical compliance**

This clinical study was designed and shall be implemented, executed and reported in accordance with the ICH GCP, with applicable local regulations (including European Directive 2001/20/EC, US CFR 21), and with the ethical principles laid down in the Declaration of Helsinki.

### **13.2 Responsibilities of the investigator and IRB/IEC**

Before initiating a trial, the investigator/institution must obtain approval/favorable opinion from the IRB for the trial protocol, written informed consent form, consent form updates, subject recruitment procedures (e.g., advertisements) and any other written information to be provided to subjects. Prior to study start, the investigator is required to sign a protocol signature page confirming his/her agreement to conduct the study in accordance with these documents and all of the instructions and procedures found in this protocol and to give access to all relevant data and records to Novartis monitors, auditors, Novartis Quality Assurance representatives, designated agents of Novartis, IRBs, and regulatory authorities as required. If an inspection of the clinical site is requested by a regulatory authority, the investigator must inform Novartis immediately that this request has been made.

### **13.3 Publication of study protocol and results**

The protocol will be registered in a publicly accessible database such as *clinicaltrials.gov*. In addition, after study completion (defined as last patient last visit) and finalization of the study report the results of this trial will be submitted for publication and posted in a publicly accessible database of clinical trial results, such as the Novartis clinical trial results website and all required Health Authority websites (e.g., *clinicaltrials.gov*).

For details on the Novartis publication policy including authorship criteria, please refer to the Novartis publication policy training materials that are provided prior to study start.

### **13.4 Quality Control and Quality Assurance**

Novartis maintains a robust Quality Management System that includes all activities involved in quality assurance and quality control, to ensure compliance with written Standard Operating Procedures as well as applicable global/local GCP regulations and ICH Guidelines.

Audits of investigator sites, vendors, and Novartis systems are performed by auditors, independent from those involved in conducting, monitoring or performing quality control of the clinical trial. The clinical audit process uses a knowledge/risk based approach.

Audits are conducted to assess GCP compliance with global and local regulatory requirements, protocols and internal standard operating procedures, and are performed according to written Novartis processes.

## **14 Protocol adherence**

This protocol defines the study objectives, the study procedures and the data to be collected on study participants. Additional assessments required to ensure safety of subjects should be

administered as deemed necessary on a case-by-case basis. Under no circumstances including incidental collection is an investigator allowed to collect additional data or conduct any additional procedures for any purpose involving any investigational drugs under the protocol, other than the purpose of the study. If despite this interdiction prohibition, data, information, observation would be incidentally collected, the investigator shall immediately disclose it to Novartis and not use it for any purpose other than the study, except for the appropriate monitoring on study participants.

[figure not shown]
Investigators ascertain they will apply due diligence to avoid protocol deviations. If an investigator feels a protocol deviation would improve the conduct of the study this must be considered a protocol amendment, and unless such an amendment is agreed upon by Novartis and approved by the IRB and health authorities, where required, it cannot be implemented.

#### **14.1 Protocol Amendments**

Any change or addition to the protocol can only be made in a written protocol amendment that must be approved by Novartis, health authorities where required, and the IRB prior to implementation.

Only amendments that are required for subject safety may be implemented immediately provided the health authorities are subsequently notified by protocol amendment and the reviewing IRB is notified.

Notwithstanding the need for approval of formal protocol amendments, the investigator is expected to take any immediate action required for the safety of any subject included in this study, even if this action represents a deviation from the protocol. In such cases, Novartis should be notified of this action and the IRB at the study site should be informed according to local regulations.

## **16 Appendices**

Not applicable.

	5.1.1 AE date imputation	22
	5.1.2 Concomitant medication date imputation	24
	5.2 Statistical models.....	25
	5.2.1 Primary analysis and supportive analyses.....	25
	5.2.2 Secondary analysis	27
	█	30
	5.3 Rule of exclusion criteria of analysis sets.....	32
6	Reference.....	36

List of abbreviations

AE	Adverse event
ATC	Anatomical Therapeutic Classification
BCDVA	Best-corrected distance visual acuity
BP	Blood pressure
CIR	Copy Increment from Reference
CMH	Cochran-Mantel-Haenszel
CSR	Clinical Study report
DCNVA	Distance-corrected near visual acuity
FAS	Full Analysis Set
ECG	Electrocardiogram
ETDRS	Early Treatment Diabetic Retinopathy Study
eCRF	Electronic Case Report Form
IRT	Interactive Response Technology
IVR	Interactive Voice Response
MAR	Missing At Random
	
MedDRA	Medical Dictionary for Drug Regulatory Affairs
MMRM	Mixed effect Model Repeat Measurement
RAP	Report and Analysis Process
PD	Protocol Deviation
SAE	Serious Adverse Event
SAF	Safety Set
SAP	Statistical Analysis Plan
SOC	System Organ Class
TEAE	Treatment Emergent Adverse Event
TESAE	Treatment Emergent Serious Adverse Event
TFLs	Tables, Figures, Listings
WHO	World Health Organization

1 Introduction

[figure not shown]
The purpose of the Statistical Analysis Plan (SAP) is to describe the implementation of statistical analysis planned in the study protocol, and to provide detailed statistical methods that will be used for the Clinical Study Report (CSR) of study CUNR844A2203.

The analysis will be conducted on all subject data at the time the study ends.

Data will be analyzed according to the data analysis plan described in this document that will be incorporated into Section 9.7 and Appendix 16.1.9 of the CSR.

1.1 Study design

Figure 1-1 Study Design

This is a multi-center, double-masked, placebo-controlled, randomized, parallel-group study. The total duration of the study will be approximately 3 months ([Figure 1-1](#)). Approximately 120 presbyopic subjects will be enrolled into the study.

Screening and Baseline: Subjects will be screened for eligibility followed by a baseline visit after which they will be randomized to receive either lipoic acid choline ester chloride (UNR844-Cl) or placebo, dosed one drop in each eye twice-daily for 3 months.

Randomization will be stratified based on binocular distance-corrected near visual acuity (DCNVA) (59 Early Treatment Diabetic Retinopathy Study [ETDRS] letters or less; 60 ETDRS letters or more) and age (45 to 50 years, 51 to 55 years and 56 to 65 years) at baseline.

Subjects will be randomized 1:1 within each stratum to either UNR844-Cl or placebo.

Randomized subjects will attend the following study visits after baseline: at Week 2, Month 1, Month 2 and Month 3.

[figure not shown]
The primary objective of this study is to evaluate the efficacy of topical UNR844-Cl ophthalmic solution in presbyopic subjects aged 45 to 55 years by assessing the change in binocular DCNVA from baseline when compared to placebo after three months of treatment.

[figure not shown]
There is no interim analysis planned.

1.2 Study objectives and endpoints

Table 1-1 Objectives and related endpoints

Objectives	Endpoints
Primary objective	Endpoint for primary objective

 Assess the efficacy of UNR844-C1 on binocular DCNVA in presbyopic subjects aged 45 to 55 years 	
 Change from baseline in binocular DCNVA in subjects aged 45 to 55 years at Month 3 after UNR844-C1 or placebo treatment
Secondary objectives	Endpoints for secondary objectives

 Assess the efficacy of UNR844-C1 on achieving 75 or more ETDRS letters in binocular DCNVA in presbyopic subjects aged 45 to 55 years Evaluate the safety of UNR844-C1 in presbyopic subjects 	
 Proportion of subjects aged 45 to 55 years achieving 75 or more ETDRS letters in binocular DCNVA at Month 3 after UNR844-C1 or placebo treatment Frequency of treatment-emergent adverse events and treatment-emergent serious adverse events in all subjects after UNR844-C1 or placebo treatment

2 Statistical methods

2.1 Data analysis general information

The analysis will be performed by the Biostatistics and statistical programming groups of Novartis, using SAS 9.4.

For categorical variables, frequencies and percentages will be computed. For continuous variables, descriptive statistics, including number of non-missing observations, mean, standard deviation, median, and range will be produced, where appropriate, point estimates and confidence intervals of treatment group differences will be provided.

These summary statistics will be presented by treatment group unless otherwise specified.

The randomization stratification factors in general will be included as factors in the primary efficacy analysis, and the corresponding supportive analyses.

2.1.1 General definitions

2.1.1.1 Study treatment

Any drug administered to the study participants as part of the required study procedures, including investigational drug and control, which are:

- Topical UNR844-Cl ophthalmic solution 1.5%, administered as one drop in each eye twice a day for three months
- Placebo (vehicle ophthalmic solution), administered as one drop in each eye twice a day for three months

2.1.1.2 Baseline and post-Baseline

Baseline (Day 1) is the date of randomization. The baseline value for efficacy and safety variables is the last available value collected prior to or at the first date of study treatment.

All data collected after the first date of treatment are defined as *post-baseline*. The *study day* for a baseline or post-baseline scheduled or unscheduled visit is defined as:

Study day = (Date of visit) – (Date of randomization) + 1;

The *study day* for a scheduled or unscheduled visit before baseline is defined as

Study day = (Date of visit) – (Date of randomization).

2.1.1.3 End of study/end of treatment/unscheduled visit day mapping

The *end of study* date (from ‘Study disposition’ CRF) is the date when a subject completes or discontinues the study. The *end of treatment* date (from ‘Treatment disposition’ CRF) is the date of the last study treatment prior to/on the end of study date. For reporting data by visit in outputs, the end of study with discontinuation (Subject status from ‘Study disposition’ CRF NOT being ‘Completed’)/end of treatment with discontinuation (Subject status from ‘Treatment disposition’ CRF NOT being ‘Completed’)/unscheduled visit date will be allocated to the nearest planned main visit, by a 1/3 – 2/3 rule. To be more specific, suppose such a visit falls in two adjacent scheduled visits (e.g., visits A and B) of an assessment corresponding to visit days of X and Y. If the assessment day of such a visit falls within rounding ($1/3 * (Y - X + 1)$) after Day X, then it will be allocated to visit A, and to visit B otherwise. [Figure 2-1](#) shows a graphical illustration of how this 1/3 – 2/3 rule of visit allocation is done. [Table 2-1](#) shows an example of the allocation of end of study/end of treatment/unscheduled visit to a scheduled main visit, when an assessment is scheduled to be done at every scheduled visit; and [Table 2-2](#) shows another example of visit allocation when an assessment is only done at Baseline, Month 1, 2 and 3.

Figure 2-1 Graphical illustration of visit allocation using the 1/3 – 2/3 rule

[figure not shown]

Table 2-1 Allocation of end of study/end of treatment/unscheduled visit for an assessment to be done at each scheduled visit

Scheduled main visit name/label	Scheduled visit study day	Scheduled visit window in days	Comment
Screening	-7	-7 – -1	Screening
Baseline	1	1	Baseline
W2	14	2 – 19	
M1	30	20 – 35	
M1.5	45	36 – 50	
M2	60	51 – 65	
M2.5	75	66 – 80	
M3	90	>= 81	

Table 2-2 Allocation of end of study/end of treatment/unscheduled visit for an assessment to be done at Baseline, Month 1, 2 and 3

Scheduled main visit name/label	Scheduled visit study day	Scheduled visit window in days	Comment
Baseline	1	1	Baseline
M1	30	2 – 40	
M2	60	41 – 70	
M3	90	>= 71	

After allocation, if the nearest planned main visit already exists: for assessments with continuous scale, the mean value of all values from the scheduled planned main visit, and the end of study/end of treatment/unscheduled visit(s) allocated to that main visit will be used for tabulation or analyses by visit; for assessments with binary/categorical scale: data of the allocated value will only be used for tabulation and analyses by visit, if data of the corresponding scheduled visit is missing. If there are multiple entries of data for a scheduled visit of an assessment with binary/categorical scale, the last entry of the data will be used.

